7.0 Statistical Considerations

Overview

The primary objective of this study will be to assess the safety of lenalidomide alternating with ipilimumab in stem cell transplantation. Patients will receive lenalidomide alternating with ipilimumab for 8 cycles (lenalidomide for 21 days, then one dose of ipilimumab, then repeat lenalidomide 4 weeks later, etc.). The starting and highest allowable dose of lenalidomide in this study will be 10 mg/d. Dose reductions to 5 mg may be allowed within patient based on clinical practice. Ipilimumab is fixed at 3 mg/kg. If the starting combination of lenalidomide 10 mg/d and ipilimumab 3 mg/kg results in toxicity, as defined below in the toxicity monitoring rule, in the first 3 of 3 patients, subsequent patients will be started at a lower combination dose of lenalidomide 5 mg/d and ipilimumab 3 mg/kg.

Secondary objectives include assessing overall response rate, overall survival, progression-free survival, and the cumulative incidence of acute and chronic GVHD with the competing risk of relapse in allogeneic transplant patients.

Safety Monitoring

We expect to accrue a total of 40 transplant patients onto two arms: Autologous (N=25) and allogeneic (N=15). All patients will receive lenalidomide alternating with ipilimumab (L+I). Each transplant arm will be monitored separately using monitoring rules for toxicity. The following stopping rules and boundaries were developed using the Multc Lean Desktop application (version 2.1.0) in the Biostatistics department.

The Principal Investigator and assigned Research Nurse will review the enrolled patients monthly while on active treatment to assess adverse events and stopping rules. The Biostatistician will be consulted as necessary. The data monitoring plan will be provided by the MD Anderson IND Office. This office is responsible to monitor the protocol conduct and data entry.

Toxicity monitoring rules: Each transplant arm (either autologous or allogeneic) will be monitored separately for toxicity. If there is a high probability of observing more than a 30% toxicity rate in either arm, that arm will be stopped. Toxicity for this stopping rule will include the following, at any time during active study treatment, which is defined as the first eight cycles plus 30 days following the last dose of study drug:

- Any grade 4 hematological toxicity at least probably related to study drug that does not resolve within 2 weeks

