- Any immune-mediated reaction to ipilimumab that requires permanent cessation of the drug

- Any other grade 3-5 organ toxicity at least probably related to study drug
- (Allogeneic arm only) Any acute grade III or higher GVHD.

Bayesian sequential monitoring⁷ will be employed to perform interim safety monitoring targeting a toxicity rate of not more than 30%. Patients will be monitored in cohorts of 1.

Autologous Arm

For the autologous arm, accrual will be stopped early if

$$\Pr [\text{prob(toxicity)} > 0.30 \mid \text{data}] > 0.975$$

That is, if we determine that there is a greater than 97.5% chance that the toxicity rate is greater than 30% in this arm, then accrual will be stopped. We assume a beta (0.6, 1.4) prior distribution for the toxicity rate, which has a mean of 0.3 corresponding to the 30% target toxicity rate. Stopping boundaries corresponding to this probability criterion are to terminate accrual in autologous patients if

If there are this many (or more) patients in the autologous transplant arm with Toxicity	Stop the arm if this many patients in the arm
3	3
4	4-5
5	5-7
6	6-9
7	7-11
8	8-13
9	9-16
10	10-18
11	11-21
12	12-23
13	13-24
14	ALWAYS STOP

Patients must complete at least two cycles of treatment or have toxicity to be included in the rule. Patients who complete at least two cycles but drop out without experiencing toxicity will be included but not counted as toxicities. If accrual onto this arm is stopped, the study will continue enrolling patients to the allogeneic transplant arm.

The rule will reset at lenalidomide 5 mg if the first 3 of 3 patients at the combination 10 mg lenalidomide dose experience toxicity. If the rule resets after the first three patients, we will continue to enroll up to 25 patients in the autologous arm at the lower combination dose using lenalidomide 5 mg. The Biostatistical collaborator will be consulted as necessary.

The operating characteristics of this rule are shown below.

Table 1. Operating Characteristics for Toxicity Stopping Rule in Autologous Arm

If the true toxicity rate is...	Early Stopping Probability	Achieved Sample Size Percentiles		
		25th	50th	75th
0.1	0.0014	25	25	25
0.2	0.0163	25	25	25
0.3	0.0891	25	25	25
0.4	0.3013	18	25	25
0.5	0.6324	7	16	25
0.6	0.8929	5	9	16
0.7	0.9872	3	5	9

Allogeneic Arm

For the allogeneic arm, accrual will be stopped early if

$$\Pr [\text{prob(toxicity)} > 0.30 \mid \text{data}] > 0.95$$

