That is, if we determine that there is a greater than 95% chance that the toxicity rate is greater than 30% in this arm, then accrual for this arm will be stopped. We assume a beta (0.6, 1.4) prior distribution for the toxicity rate, which has a mean of 0.3 corresponding to the 30% target toxicity rate. Stopping boundaries corresponding to this probability criterion are to terminate accrual in allogeneic patients if

If there are this many (or more) patients in the allogeneic transplant arm with Toxicity	Stop the arm if this many patients in this arm
3	3-4
4	5-6
5	7-9
6	10-11
7	12-13
8	14-15
9	ALWAYS STOP

Patients must complete at least two cycles of treatment or have toxicity to be included in the rule. Patients who complete at least two cycles but drop out without experiencing toxicity will be included but not counted as toxicities. If accrual onto this arm is stopped, the study will continue enrolling patients to autologous arm.

The rule will reset at lenalidomide 5 mg if the first 3 of 3 patients at the combination 10 mg lenalidomide dose experience toxicity. If the rule resets after

the first three patients, we will continue to enroll up to 15 patients in the allogeneic arm at the lower combination dose using lenalidomide 5 mg. The Biostatistical collaborator will be consulted as necessary.

The operating characteristics of this rule are shown below.

Table 2. Operating Characteristics for Toxicity Stopping Rule in Allogeneic Arm

If the true toxicity rate is...	Early Stopping Probability	Achieved Sample Size Percentiles		
		25th	50th	75th
0.1	0.0016	15	15	15
0.2	0.0210	15	15	15
0.3	0.0998	15	15	15
0.4	0.2780	14	15	15
0.5	0.5367	7	12	15
0.6	0.7866	3	7	12
0.7	0.9406	3	5	7

Primary Objective

We will estimate the toxicity rate in each arm along with a corresponding 95% credible interval. In addition, toxicity will be summarized by arm, type, and grade.

Secondary Objectives

For secondary objectives, we will estimate response at the end of eight cycles and overall with a 95% confidence interval. We will also estimate specific response types such as humoral and cellular. This data will be used to inform future studies using higher dose combinations. With 15 patients assigned to a transplant arm, if the response rate is 20%, an asymptotic 95% confidence interval will be (0, 0.402). With 25 patients assigned to a transplant arm, if the response rate is 20%, an asymptotic 95% confidence interval will be (0.043, 0.357).

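### The printed allogeneic stopping boundaries do not follow from the stated prior and 95% criterion, and Table 2 describes the criterion rather than the boundaries

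*Combined protocol and SAP*

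**What the plan says.** All of this is in section 7.0, under the toxicity monitoring rules and the Allogeneic Arm.

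- **Target and looks.** The plan describes "interim safety monitoring targeting a toxicity rate of not more than 30" percent, and "Patients will be monitored in cohorts of 1".
- **Prior.** "We assume a beta (0.6, 1.4) prior distribution for the toxicity rate, which has a mean of 0.3 corresponding to the 30% target toxicity rate".
- **Criterion.** Accrual stops when the posterior probability of a rate above 0.30 exceeds 0.95. In words: "That is, if we determine that there is a greater than 95% chance that the toxicity rate is greater than 30% in this arm".
- **Boundaries.** The table is introduced by "Stopping boundaries corresponding to this probability criterion are to terminate accrual in allogeneic patients if". It reads (toxicities: patients) 3: 3-4; 4: 5-6; 5: 7-9; 6: 10-11; 7: 12-13; 8: 14-15; 9: always stop.
- **Operating characteristics.** "Table 2. Operating Characteristics for Toxicity Stopping Rule in Allogeneic Arm" gives early-stopping probabilities of 0.0016, 0.0210, 0.0998, 0.2780, 0.5367, 0.7866 and 0.9406 at true rates 0.1 to 0.7.
- **Sample sizes.** "Autologous (N=25) and allogeneic (N=15".

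**The concern.** The criterion, the boundary table and Table 2 are presented as three views of one rule. With the prior given, the criterion fixes the boundaries and the boundaries fix Table 2, so each can be checked against the others. The boundary table does not agree with the other two.

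This is the main safety rule of the arm in a study whose primary objective is safety. The investigator and research nurse review the stopping rules monthly, and the biostatistician is consulted only as needed, so the printed table is the natural working tool. At 3 toxicities in 4 patients, an early and plausible result, the table closes the arm and the formula keeps it open. The plan does not say which governs. The false-stopping and detection rates shown to those who approved the plan would also not be those of the rule in use.

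**Working it through.** **Inputs (all from section 7.0).** Prior beta(0.6, 1.4); target 0.30; cut-off 0.95 (allogeneic) or 0.975 (autologous); cohorts of 1; N = 15 or 25.

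**Formula.** After x toxicities in n patients the posterior is beta(0.6 + x, 1.4 + n − x). The boundary at each n is the smallest x with Pr(rate > 0.30) above the cut-off. Early-stopping probabilities come from exact forward recursion over binomial paths, removing paths that reach the boundary. The last patient is not counted as a look, because accrual is then complete.

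**Step 1: check the method on the autologous arm.** At 0.975 and N = 25, this gives every printed autologous boundary (n = 3 to 24) and every Table 1 percentile. The stopping probabilities also match, except 0.3014 against 0.3013 at a true rate of 0.4.

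**Step 2: reproduce Table 2 from the stated criterion.** At 0.95 with looks through n = 14, early stopping is 0.0016, 0.0210, 0.0998, 0.2780, 0.5367, 0.7866 and 0.9406. All seven values equal Table 2.

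**Step 3: compare the boundaries.**

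| Toxicities | Patients, by the criterion | Patients, as printed | Printed point not above 0.95 |
|---|---|---|---|
| 3 | 3 | 3-4 | 3/4: 0.935 |
| 4 | 4-5 | 5-6 | 4/6: 0.945 |
| 5 | 6-8 | 7-9 | 5/9: 0.922 |
| 6 | 9-10 | 10-11 | 6/11: 0.938 |
| 7 | 11-12 | 12-13 | 7/13: 0.94999 |
| 8 | 13-14 | 14-15 | none (8/15: 0.960) |

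In the first five rows the upper limit is one patient beyond what the criterion allows. In the last row, 8/15 does exceed 0.95, but n = 15 is the end of accrual and is not a look in Table 2.

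**Step 4: could another cut-off explain the printed table?** Not with this prior. Stopping at 5/9 needs a cut-off below 0.922, while continuing at 7/14 (0.9245) and 2/2 (0.928) needs a higher one.

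**Step 5: operating characteristics of the printed boundaries (looks through n = 14).**

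| True rate | Table 2 | Printed boundaries |
|---|---|---|
| 0.1 | 0.0016 | 0.0047 |
| 0.2 | 0.0210 | 0.0451 |
| 0.3 | 0.0998 | 0.1676 |
| 0.4 | 0.2780 | 0.3850 |
| 0.5 | 0.5367 | 0.6428 |
| 0.6 | 0.7866 | 0.8520 |
| 0.7 | 0.9406 | 0.9629 |

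At 0.30 the ratio is 0.1676 / 0.0998 = 1.68. Adding a look at n = 15 raises the printed-boundary figure at 0.30 to 0.1722. At a true rate of 0.5 the median sample size is 9 under the printed boundaries, against 12 in Table 2 and under the criterion.

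**Step 6: Table 2 percentiles (25th/50th/75th).** Three rows fit neither rule.

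| True rate | Table 2 | Criterion | Printed boundaries |
|---|---|---|---|
| 0.4 | 14/15/15 | 12/15/15 | 8/15/15 |
| 0.6 | 3/7/12 | 5/8/14 | 4/6/9 |
| 0.7 | 3/5/7 | 3/5/8 | 3/4/6 |

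A 25th percentile of 3 at a rate of 0.6 is impossible. The only stop by the third patient is 3 of 3, with probability 0.6³ = 0.216, which is below 0.25.

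**The case against.** The strongest reply is that this is one mis-shifted table in a small pilot arm and that it errs on the safe side. From the second row on, each printed range is the criterion's range moved up by one patient, which looks like a transcription slip. The criterion, prior and Table 2 stopping probabilities agree with each other. The printed table also detects excess toxicity more often: 0.643 against 0.537 at a true rate of 0.5. All of that is correct. It describes the origin and direction of the error but does not remove the contradiction.

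Four narrower points also have merit:

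- The 7 of 13 point fails only on the strict inequality. The other four discrepancies are not rounding.
- That staff would follow the table rather than the formula is an inference from the monthly review arrangement, not something the plan states.
- The match with Table 2 needs the n = 15 look to be left out. With it, the criterion gives 0.1096 at 0.30. The printed boundaries on the same footing give 0.1722, so the gap remains.
- Three toxicities in the first three patients at the starting dose reset the rule instead of closing the arm, and neither calculation includes this. That path has probability 0.3³ = 0.027 at a rate of 0.30 and is common to both. Without it the figures are 0.0998 − 0.027 = 0.073 and 0.1676 − 0.027 = 0.141, so the difference is unchanged.

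**Conclusion.** The concern holds. Four printed stop points clearly fail the stated criterion and a fifth fails marginally. Table 2's stopping probabilities belong to the criterion, not to the printed boundaries. Under the printed boundaries, the chance of early stopping at an acceptable 30% rate is 16.8% against a stated 9.98%, about 7 percentage points more. At a 20% rate it is 4.5% against 2.1%. Patients are not exposed to added risk by the error. The harm is that an arm may be closed without meeting its pre-specified criterion, and that the approved operating characteristics are not those of the table.

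These figures assume that the printed table is the one applied, that outcomes are known after each patient before the next look, that there is no look at n = 15, and that the reset is left out. The boundary discrepancy itself needs only the prior and the cut-off. Because a decision threshold is wrong as written, it must be fixed.

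**What to change.** Reconcile the criterion, the boundary table and Table 2 by one of two routes.

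1. **Keep the stated criterion.** Regenerate the allogeneic boundaries from the beta(0.6, 1.4) prior and the 0.95 cut-off. In the format of the autologous table they are 3: 3; 4: 4-5; 5: 5-8; 6: 6-10; 7: 7-12; 8: 8-14; 9: always stop. Keep Table 2's stopping probabilities and correct its percentiles to 12/15/15 at 0.4, 5/8/14 at 0.6 and 3/5/8 at 0.7.
2. **Keep the printed boundaries.** Restate the criterion, since no single cut-off with this prior yields them, and replace Table 2 with the operating characteristics of that rule (Steps 5 and 6 of the working).

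In either case, state whether the last patient counts as a look and whether the table or the formula governs if they differ.

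The cost is a corrected table in a protocol amendment. The maximum of 15 and the study procedures do not change. Under the first route the arm would tend to enrol longer when toxicity is high than under the printed table (median 12 against 9 at a true rate of 0.5). That is what Table 2 already tells its readers, but the sponsor should make the choice knowingly.

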3.0 Eligibility

3.1 Inclusion Criteria

- a. Age \geq 18 years to \leq 80 years.
- b. Hematologic or lymphoid malignancy.
- c. Autologous patients can be included anytime within 6 months post-transplant, if they had no signs of progression and meet one of the following criteria:⁸⁻⁹
 - i. Leukemia
 - ii. Lymphoma (all types of B and T cell lymphoma)
 - iii. Multiple myeloma
- d. Allogeneic patients if:
 - i. Patients had engrafted donor cells (i.e., > 20% donor T-cell from PB/PCR); and,
 - ii. Patients NOT in CR after their allogeneic transplant, and off tacrolimus and/or mycophenolate mofetil for at least 3 to 4 weeks with no signs of GVHD; or,
 - iii. Patients had evidence of relapse after their transplant who are off tacrolimus and/or mycophenolate mofetil or other immunosuppressants for GVHD for 3 to 4 weeks with no signs of GVHD (Prednisone doses \leq 10 mg are permitted as stated previously).
- e. No active infection.
- f. ANC \geq 1.5 x 10⁹/L; platelets \geq 50 x 10⁹/L.
- g. Able to adhere to the study visit schedule and other protocol requirements.
- h. Performance status: ECOG 2 or less or Karnofsky of at least 60.
- i. Cardiac EF \geq 45% by 2D-ECHO within 3 months of study entry (or within 1 month if received chemotherapy within the past 3 months).
- j. FEV1, FVC and DLCO \geq 40% within 3 months of study entry (or within 1 month if received chemotherapy within the past 3 months).
- k. Serum creatinine \leq 1.6 mg/dL and creatinine clearance \geq 30 ml/min. Creatinine clearance will be calculated using the Cockcroft-

Gault equation: Use actual body weight if it is less than or equal to ideal body weight. Use ideal body weight if patient greater than ideal body weight, but is less than or equal to 50% over ideal body weight. Use adjusted body weight if patient is greater than 50% over ideal body weight.

- I. Liver function tests (unless related to Gilbert's disease or medications)
 - i. SGPT, SGOT less than 2x the upper limit of normal range.
 - ii. Direct Bilirubin <1.6
- m. Patient or legally authorized representative able to sign informed consent.
- n. Females of childbearing potential (FCBP)† must have a negative serum or urine pregnancy test with a sensitivity of at least 50 mIU/mL within 10 - 14 days prior to study entry.

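### The response analysis shows only the Wald interval, which under-covers at 15 and 25 patients, and lets a persisting transplant remission count as a response in autologous myeloma patients

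*Combined protocol and SAP*

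**What the plan says.** Section 7.0, Secondary Objectives, states the analysis in one sentence: "we will estimate response at the end of eight cycles and overall with a 95% confidence interval". No interval method is given there. Two precision examples follow: "With 15 patients assigned to a transplant arm, if the response rate is 20%, an asymptotic 95% confidence interval will be (0, 0.402" and "With 25 patients assigned to a transplant arm, if the response rate is 20%, an asymptotic 95% confidence interval will be (0.043, 0.357" (closing brackets omitted). Of the results it adds: "This data will be used to inform future studies using higher dose combinations".

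Section 7.0 does say who counts for toxicity monitoring: "Patients must complete at least two cycles of treatment or have toxicity to be included in the rule". It has no matching statement for response.

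On status at entry, Section 3.1c reads "Autologous patients can be included anytime within 6 months post-transplant, if they had no signs of progression", and lists multiple myeloma among the eligible diseases. For the allogeneic arm, Section 3.1d asks for either "Patients NOT in CR after their allogeneic transplant" or "Patients had evidence of relapse after their transplant who are off tacrolimus" (the sentence continues).

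Section 5.0 sets out the myeloma response criteria in full and refers other diseases to Appendix I, which is not in the text available for this review.

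**The concern.** There are two separate problems with how a response rate from this trial would be read.

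First, an analyst looking for a method finds only the asymptotic one. With 15 or 25 patients and a modest response rate, a Wald interval contains the true rate less often than 95% of the time, and most misses are upper limits that are too low. With no responders it has zero width.

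Second, autologous patients start study drug within six months of a transplant that may itself have produced a remission. If the response definition is a state rather than a change from entry, a remission that simply lasts is credited to study drug. No decision rule uses response, so what is at stake is how the rate is interpreted, including any use of it in planning later studies.

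**Working it through.** **1. Reproducing the plan's intervals.** Inputs from Section 7.0: p = 0.20, n = 15 and 25. Wald is p ± 1.96·√(p(1−p)/n).
- n = 15: 0.2 ± 1.96·√(0.16/15) = (−0.0024, 0.4024), which is (0, 0.402) when cut at 0.
- n = 25: 0.2 ± 1.96·√(0.16/25) = (0.0432, 0.3568).

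Both match the plan.

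**2. Exact Wald coverage.** For a true rate p, add the binomial probabilities of every responder count whose interval contains p.
- p = 0.20, n = 15: counts 2 to 6 cover. The upper limit is too low with probability 0.167 (0 or 1 responder) and the lower limit too high with probability 0.018 (7 or more). Coverage is 81.5%.
- p = 0.20, n = 25: counts 3 to 9 cover. The misses are 0.098 and 0.017. Coverage is 88.4%.

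Coverage moves in a saw-tooth, and 20% is near a trough at n = 15 (94.4% at p = 0.19), so a range is fairer. Equal weights on p = 0.10 to 0.30 in steps of 0.001:

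| | n = 15 | n = 25 |
|---|---|---|
| Wald, mean (min to max) | 88.9% (79.2-95.0) | 90.9% (80.2-95.6) |
| Wald, mean chance upper limit is below p | 9.8% | 7.8% |
| Wald, mean chance lower limit is above p | 1.3% | 1.3% |
| Wilson, mean (min) | 95.7% (91.5) | 95.4% (92.3) |
| Clopper-Pearson, mean (min) | 98.1% (96.6) | 97.5% (95.5) |

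Over higher true rates of 26-65% at n = 25, mean Wald coverage is 93.0%, so the shortfall is smaller there.

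**3. Zero responders.** Wald gives (0, 0). The upper limits for 0/15 are 0.204 (Wilson) and 0.218 (Clopper-Pearson); for 0/25 they are 0.133 and 0.137. At a true rate of 10%, zero responders has probability 0.9^15 = 0.206 and 0.9^25 = 0.072.

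**4. The same examples by other methods.** Wilson is [p + z²/2n ± z·√(p(1−p)/n + z²/4n²)] / (1 + z²/n), with z² = 3.8415.
- 3/15: (0.32805 ± 0.23953)/1.25610 = (0.070, 0.452).
- 5/25: (0.27683 ± 0.17461)/1.15366 = (0.089, 0.391).

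Clopper-Pearson gives (0.043, 0.481) and (0.068, 0.407).

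**5. Entry status against the response definition (myeloma).**
- Section 3.1c requires absence of progression. CR or VGPR after transplant satisfies that.
- In Section 5.0, CR needs negative immunofixation, a marrow plasma-cell limit and no soft tissue plasmacytoma. The first VGPR item needs M protein seen on immunofixation only. These are states.
- The timing rule asks for two assessments in a row at any time, with no condition on status at entry.

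A patient who enters in CR and stays in CR therefore meets the written CR definition.

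**6. Size of the second problem.** Let s be the share of the autologous arm who are myeloma patients in remission at entry, k the chance that the remission persists, and r the new-response rate in everyone else. The reported rate is s·k + (1−s)·r, which exceeds r by s·(k−r). None of s, k or r is in the documents, so all are assumptions. Each such patient among 25 adds (k−r)/25. With k = 0.80 and r = 0.20 this is 0.60/25 = 2.4 percentage points. With k from 0.60 to 0.95 and r from 0.10 to 0.30 it runs from 0.30/25 = 1.2 to 0.85/25 = 3.4 points. If no such patient enrols, it is zero.

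**The case against.** **The plan never adopts Wald.** The examples illustrate precision, are labelled asymptotic and are correct. That stands: a reader might infer that the plan commits to Wald or has miscalculated, and the text supports neither. Nor is planned precision overstated in width, since Wilson is slightly narrower (0.381 against 0.402 at 3/15; 0.303 against 0.314 at 5/25). What remains is that no other method is offered.

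**Wilson is not better everywhere.** True. At a 30% rate it covers 91.5% and 92.3%, against 95.0% and 94.9% for Wald, and at 20% with n = 25 it covers 92.6%. Its advantage is on average and near zero responders.

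**A denominator is implied.** Both examples speak of patients assigned to an arm, which points to everyone assigned. But this wording sits in a precision example. It does not settle how to count patients removed for progression or intolerable side effects (Sections 9.2 and 9.3) before eight cycles.

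**Remission is handled elsewhere.** The PD criteria refer to baseline, relapse from CR is defined, and progression-free survival is planned. These capture loss of remission; they do not stop a retained one from counting as a response.

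**The allogeneic arm and other diseases.** A reader might extend the second problem to both. The allogeneic criteria ask for patients not in CR or with relapse. The case of a relapse re-treated into CR before entry rests only on the text's silence. For other diseases, Appendix I may already set an entry-status rule.

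**Conclusion.** The point holds in limited form, with low to moderate priority because response is secondary, descriptive and tied to no decision rule.

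If the only illustrated method is used, nominal 95% intervals cover 81.5% (n = 15) and 88.4% (n = 25) at the plan's own 20% rate. The means of 88.9% and 90.9% rest on an evenly weighted 10-30% range chosen for this review.

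For autologous myeloma patients, the written criteria allow an unchanged post-transplant remission to count as a response. The inflation is 1.2 to 3.4 percentage points per such patient among 25, under the assumed ranges shown. A large inflation for the whole autologous arm is not supported: it would need a high share of myeloma patients in remission at entry, and the documents give no such share. The two problems also partly offset, because a rate raised by persisting remissions lies where Wald performs better.

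**What to change.** **Interval.** State in Section 7.0 that all response rates use the Wilson interval, or Clopper-Pearson if coverage must never fall below 95%. Restate the examples: Wilson (0.070, 0.452) for 3/15 and (0.089, 0.391) for 5/25; Clopper-Pearson (0.043, 0.481) and (0.068, 0.407). This is a wording change only. Clopper-Pearson is wider (0.438 and 0.339).

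**Entry status.** For myeloma, record status at entry from the baseline work-up already listed in Section 5.0. Count as a response only an improvement in category from that status, so that a VGPR that merely persists does not count. Report patients in CR at entry separately by progression-free survival. Apply the same rule to other diseases unless Appendix I already sets one.

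**Denominator.** Define it as all treated patients in the arm who are not in CR at entry, with patients who stop early or cannot be assessed counted as non-responders.

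**Cost.** One recorded field and a counting rule. For diseases other than myeloma, Section 5.0 lists no baseline marrow or imaging, so status would come from the eligibility assessment, which may not be close to first dose. The denominator shrinks and the interval widens: if 5 of 25 patients were in CR at entry, Wilson at a 20% rate would be (0.081, 0.416) for 4/20, against (0.089, 0.391) for 5/25.
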